8.3.10.4.1. Daily Ordinal Clinical Outcomes from D5V, D11V, and D28V

Using similar definitions for clinical improvement and most severe solicited event as those provided in Section 6.5, daily values of clinical improvement status, maximum severity of solicited symptoms, and presence of any medically attended visits will be calculated D5V, D11V, and D28V as described in Section 6. Since solicited events were to be collected up to Day 11, maximum severity of solicited events post baseline will be used in deriving the most severe solicited event to be used for D28V OCO. The OCO for each

outcome for D5V and D11V will be calculated based on the algorithm in Section 6.5.4. Similarly, the OCO for D28V will be calculated by replacing D5V by D28V in the algorithm described in Section 6.5.4.

The OCOs from the above three timepoints will be presented using two graphical presentations. First a bar plot of the percentage of subjects falling in each of the OCO categories will be presented by timepoint (D5V, D11V, D28V) and separately for each treatment group for the ITT population in Figure 24. The missing OCO category will also be added to the figure. Second, a heatmap plot of individual subject's OCO will be plotted for each day, and separate plots will be generated for the two treatment groups as presented in Figure 26. Subjects will be ordered in the heatmap figure such that subjects with the best outcome (i.e. lower values of OCO) appear at the bottom and subjects with the worst outcome or missing OCO appear at the top.

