6.5.3. Most Severe Solicited Event for DOOR

If a subject had severity grades (0 to 3) recorded for every solicited event (abdominal pain, vomiting, diarrhea, allergic reaction, and candidiasis) from Study day 1 to D5V Study day, inclusive, then the most severe solicited event at D5V, a component of DOOR, will be the maximum severity grade taken across all solicited events from Study Day 1 to D5V Study Day.

If a subject had any solicited event of severity grade 3 from Day 1 to D5V Study Day, then the most severe solicited event at D5V will be grade 3, regardless of the presence of missing data during that period. Otherwise, if the subject has missing data for the severity grade of any solicited event from Day 1 to D5V study day, then most severe solicited event at D5V will be missing.

If a subject had severity grades (0 to 3) recorded for every solicited event (abdominal pain, vomiting, diarrhea, allergic reaction, and candidiasis) from study day 1 to study day 11, inclusive, then the most severe solicited event at D11V, a component of DOOR at D11V, will be the maximum severity grade taken across all solicited events from study day 1 to study day 11.

If a subject had any solicited event of severity grade 3 from Day 1 to study day 11 study day, then the most severe solicited event at study day 11 will be grade 3, regardless of the presence of missing data during that period. Otherwise, if a subject has missing data for the severity grade of any solicited event from Day 1 to study day 11 study day, then most severe solicited event at D11V will be missing.

A similar approach as described above will be used to determine the most severe solicited event at D28V by considering all solicited events reported post dose 1.

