8.3.10. Longitudinal Analysis of Clinical Improvement using DOOR for ITT Analysis Population

In order to compare patterns of clinical improvement over time, multiple longitudinal analyses based on DOOR will be performed. For each of these analyses, a different definition of DOOR will be used.

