8.3.10.4.2. DOOR Analysis Based on Ordinal Clinical Outcomes from D5V, D11V, and D11V

To construct DOOR for this analysis, an average of observed OCO across the three timepoints will be calculated for each subject ignoring missingness of data at some of the timepoints. This calculation will be based on subjects with non-missing OCO for at least one timepoint, and the average OCO calculation for each subject will ignore missingness of OCO for any of the timepoints. Next, subjects will be ranked based on their average OCO without tie-breaking.

For the DOOR analysis without tie-breaking, subjects will be ranked such that subjects with a lower average OCO are assigned a higher (better) rank while subjects with higher average ordinal clinical outcome are assigned a lower (worse) rank.

The null hypothesis corresponding to this analysis is:

H0: The sum of the probability that a subject assigned to placebo will have a higher DOOR Visit than if assigned to the Azithromycin plus one-half the probability of equal DOORs is 50% (i.e., no difference in DOOR).

The above null hypothesis can be tested using a Mann-Whitney U Test [1].

The analysis of this new DOOR will use the same approach as that described in Section 8.2.8 to estimate Prob (higher DOOR in placebo compared to Azithromycin) + $\frac{1}{2}$ Prob(no difference in DOOR). The Mann Whitney test will be used to test the differences.

Results of this DOOR analysis will be reported in Table 55.

8.3.11. Association PCT Level at Screening and Detection of a Viral or Bacterial Pathogen

The relationship between PCT level at screening and detection of a viral pathogen will be assessed using logistic regression. Analysis will be repeated with detection of a bacterial pathogen as the outcome. The Results will be reported in Table 64. Individual listing of pathogens detected is provided in Listing 22.

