9.3.1. Solicited Events and Symptoms

Solicited events will be captured from Day 1 until Day 11. For those with multiple solicited events, the ordinal response table will be based upon the most severe solicited event.

Solicited events were recorded for trial Days 1-11, or until study completion or termination, as the maximum severity for each day. Target solicited events include abdominal pain, vomiting, diarrhea, allergic reaction, and candidiasis.

The proportion of subjects in each treatment group experiencing each solicited event will be tabulated by treatment group (Table 65). The proportion of subjects in each treatment group experiencing each solicited event will be tabulated by treatment group and severity (Table 66). The proportion of subjects in each treatment group experiencing each solicited event will also be tabulated by day and severity level (Table 67 and Table 69). Finally, solicited events will be analyzed by taking the most severe response over the follow-up period, dichotomizing into a binary variable (mild or greater, moderate or greater, severe) (Table 68). Proportions for these derived binary variables will be reported along with 95% CIs using the Wilson method. Comparisons of proportions by treatment groups will be given as risk differences (with 95% CIs from the Miettinen–Nurminen method) and p-values from Fisher’s Exact Test.

The maximum severity occurrence of each solicited event (proportion of subjects for each severity level) will be plotted for each solicited adverse event (Figure 27). Solicited events by subject will also be presented (Listing 9).

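### The exploratory three-visit average outcome (SAP 8.3.10.4) scores one early moderate or severe solicited event three times, so an always-improved subject can rank below one who failed at Day 5 and recovered

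*SAP*

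**What the plan says.** SAP 9.3.1 sets the collection period: "Solicited events will be captured from Day 1 until Day 11". SAP 6.5.3 then defines the event grade that enters the OCO. For D5V it is the "maximum severity grade taken across all solicited events from Study Day 1 to D5V Study Day". For D11V it is the "maximum severity grade taken across all solicited events from study day 1 to study day 11". For D28V, "A similar approach as described above will be used to determine the most severe solicited event at D28V", namely "by considering all solicited events reported post dose 1". SAP 8.3.10.4.1 repeats the D28V rule ("maximum severity of solicited events post baseline will be used in deriving the most severe solicited event to be used for D28V OCO") and gives its reason, which is that collection stops at Day 11.

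SAP 6.5.4 maps a subject with clinical improvement to OCO 1, 2, 3 or 4 for no, mild, moderate or severe event. A subject without improvement gets 5, 6 or 7 according to medically attended events, and death is 8. Under SAP 8.3.10.4.2, "an average of observed OCO across the three timepoints will be calculated for each subject". Missing visits are ignored, a lower mean ranks better, there is no tie-break, and the arms are compared by a Mann-Whitney test in Table 55. SAP 8.3.10 states the purpose of these analyses: "In order to compare patterns of clinical improvement over time". SAP section 13 lists this one among the exploratory analyses added in the SAP.

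**The concern.** At any single visit the OCO places every improved subject, whatever the solicited event, above every non-improved subject. Averaging three cumulative grades can break that order. An event on Day 2 sets the OCO of an always-improved subject at D5V, D11V and D28V, whereas a failure at D5V that resolves on its own enters once. The D28V event component holds no information from after Day 11.

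Two things are at stake. First, the section is meant to describe improvement over time, and the score gives a past event the weight of three visits. Second, Protocol 9.2.2 describes solicited events as common and known to follow the study product, and Protocol 2.3.1 lists several of them as labelled azithromycin risks. If they are commoner on azithromycin, tripling them moves Table 55 toward placebo. Table 49 and Figures 24 and 26 would also show a subject who is well on Day 28 at level 2-4 for that visit because of an event in Days 1-11.

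**Working it through.** The plan states no figure for this score, so there is none to reproduce.

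**Score.** Mean OCO = (OCO at D5V + OCO at D11V + OCO at D28V) / 3; lower is better. Levels are from SAP 6.5.4 and event windows from SAP 6.5.3.

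Improved at all three visits, one event before D5V:

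| Event | As written | D28V carry-over removed | Event counted once |
|---|---|---|---|
| Mild | (2+2+2)/3 = 2.00 | (2+2+1)/3 = 1.67 | (2+1+1)/3 = 1.33 |
| Moderate | (3+3+3)/3 = 3.00 | (3+3+1)/3 = 2.33 | (3+1+1)/3 = 1.67 |
| Severe | (4+4+4)/3 = 4.00 | (4+4+1)/3 = 3.00 | (4+1+1)/3 = 2.00 |

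Comparators, not improved at D5V and no solicited event:

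- No medically attended event, then recovered: (5+1+1)/3 = 2.33.
- Outpatient, urgent care or ED visit not meeting the antibiotic-for-LRTI definition, then recovered: (6+1+1)/3 = 2.67.
- The same with hospitalization: (7+1+1)/3 = 3.00.
- Not improved at D5V and D11V, no medically attended event, then recovered: (5+5+1)/3 = 3.67.
- Visit with an antibiotic for LRTI. The improvement definition counts such a visit at any time after randomization, so it carries forward: (6+6+6)/3 = 6.00.

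As written, a moderate (3.00) or severe (4.00) event ranks below 2.33, and a severe event also ranks below 3.67. A mild event (2.00) does not reverse the order. Removing only the D28V carry-over leaves the severe event worse (3.00) and the moderate event tied (2.33). Counting once puts all three grades ahead of 2.33.

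**Contrast within the SAP.** The daily analysis (8.3.10.3) scores an event only on its own day. A one-day severe event with improvement on all 11 days averages (10+4)/11 = 1.27, against (10+5)/11 = 1.36 for one failed day, so the order is kept.

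**Size, by simulation.** From the documents: 337 per arm (674/2) and 57.6% improved at D5V on azithromycin. Assumed, because the documents do not give them: improvement of about 76% at D11V and 86% at D28V, within-subject correlation 0.3 to 0.6, about 36% of events moderate or severe (for example 7% of the 20% and 13% of the 35%), complete data, and non-improvement scored 5. The test is the tie-corrected two-sided Mann-Whitney at 0.05. The deficit case puts placebo 12.5 points lower at D5V only (57.6 - 12.5 = 45.1%).

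| Any event by D5V, placebo v azithromycin | Equal clinical outcomes: rejection favouring placebo, as written v counted once | Placebo 12.5 points worse at D5V only: rejection favouring azithromycin, as written v counted once |
|---|---|---|
| 20% v 35% | about 42% v 13-16% | about 3% v 22% |
| 15% v 25% | about 22% v 10% | about 11% v 31% |
| 15% v 20% | about 8% v 5% | about 25% v 39% |

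At equal event rates and equal outcomes there is no tilt (DOOR probability 0.500). In one run of the 20% v 35% equal-outcome case, rejection was 42% as written, 30% without the D28V carry-over and 14% counted once.

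**The case against.** The strongest defence is that this is a disclosed choice. The SAP gives its reason, and OCO Tables 2 and 3 already grade events cumulatively through the visit, so level 2-4 at D28V can be read as improved, with an event during follow-up. DOOR is also meant to credit the arm with fewer harms. That stands: the 42% is not a false-positive rate, since the arms do differ in events in that scenario. It does not explain why one event should count three times, or why the average should reverse the plan's own ordering of levels.

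Several stronger readings are tempting, and the documents do not support them:

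- **Any early event ranks below a Day 5 failure.** A mild event does not. A failure with an antibiotic-treated LRTI visit carries forward to 6.00, and death is 8 at every visit, so serious failures keep their weight.
- **The D28V sentence is the cause.** The D11V grade is cumulative by protocol definition and contributes at least as much.
- **The rule penalises azithromycin as such.** It applies to both arms and to events of any cause. The tilt exists only if event rates differ.
- **It could hide a placebo deficit from the trial.** SAP 8.1.1 rests non-inferiority on the primary analysis alone. Table 22 shows Day 5 improvement, Tables 52 and 53 count improvement without solicited events, Table 54 uses the daily score, and Table 49 shows the D5V failures directly.

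**Conclusion.** The point holds for this one exploratory analysis. The SAP's rules score one early moderate or severe event at all three visits in an always-improved subject, and rank that subject (3.00 or 4.00) below one with a self-resolving Day 5 failure (2.33). The D11V and D28V windows both contribute. This much follows from the text and needs no assumption.

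The effect on Table 55 does rest on assumptions. It runs toward placebo if events are commoner on azithromycin, is substantial at 20% v 35%, small at 15% v 20%, and absent at equal rates. The deficit-case figures depend further on the assumed later improvement and within-subject correlation, so they should be read as a range.

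Table 55 is to be reported against a 0.05 boundary, without multiplicity correction (SAP 6.8), so it needs a companion result. The primary non-inferiority conclusion and the protocol-defined D5V and D11V DOOR analyses are not affected.

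**What to change.** In SAP 8.3.10.4, report with Table 55 a version that counts each solicited event once, at the first visit with an observed OCO on or after the event. D5V then uses events from Day 1 to the actual D5V date. D11V uses later events to Day 11, or all events from Day 1 if the D5V OCO is missing, so that an early event is not lost. D28V uses only the clinical levels 1, 5, 6, 7 and 8. A subject with neither a D5V nor a D11V OCO would still contribute no event; state how many there are.

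In Table 49 and Figures 24 and 26, either show D28V without the Day 1-11 carry-over or label levels 2-4 there as an event during Days 1-11. Leave the protocol-defined D5V and D11V DOOR analyses unchanged.

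The cost is SAP wording and one extra derivation. In that version the D11V OCO differs from SAP Table 3 and levels 2-4 cannot occur at D28V, so it must be labelled clearly.

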8.3.10.4.2. DOOR Analysis Based on Ordinal Clinical Outcomes from D5V, D11V, and D11V

To construct DOOR for this analysis, an average of observed OCO across the three timepoints will be calculated for each subject ignoring missingness of data at some of the timepoints. This calculation will be based on subjects with non-missing OCO for at least one timepoint, and the average OCO calculation for each subject will ignore missingness of OCO for any of the timepoints. Next, subjects will be ranked based on their average OCO without tie-breaking.

For the DOOR analysis without tie-breaking, subjects will be ranked such that subjects with a lower average OCO are assigned a higher (better) rank while subjects with higher average ordinal clinical outcome are assigned a lower (worse) rank.

The null hypothesis corresponding to this analysis is:

H0: The sum of the probability that a subject assigned to placebo will have a higher DOOR Visit than if assigned to the Azithromycin plus one-half the probability of equal DOORs is 50% (i.e., no difference in DOOR).

The above null hypothesis can be tested using a Mann-Whitney U Test [1].

The analysis of this new DOOR will use the same approach as that described in Section 8.2.8 to estimate Prob (higher DOOR in placebo compared to Azithromycin) + $\frac{1}{2}$ Prob(no difference in DOOR). The Mann Whitney test will be used to test the differences.

Results of this DOOR analysis will be reported in Table 55.

8.3.11. Association PCT Level at Screening and Detection of a Viral or Bacterial Pathogen

The relationship between PCT level at screening and detection of a viral pathogen will be assessed using logistic regression. Analysis will be repeated with detection of a bacterial pathogen as the outcome. The Results will be reported in Table 64. Individual listing of pathogens detected is provided in Listing 22.

8.4. Imputation of Missing Data

8.4.1. Multiple Imputation of Missing Values of Clinical Improvement on Day 5, Day 11, and Day 28

Primary and secondary analyses using the ITT population depend on multiple imputation of clinical improvement on D5V, D11V, and D28V. First, a table showing the number and percentage of missing data for clinical improvement on D5V, D11V, and D28V will be presented in Table 20. Regardless of the percent of missingness, multiple imputation will be used for all ITT analyses. Robustness of the multiple imputation

model will be assessed by tipping point analyses. The results of this sensitivity analyses will be provided in [Table 27](#) for D5V, [Table 28](#) for D11V and [Table 29](#) for D28V. In order to use the MI model to adjust for bias caused by missing data, we assume that data is missing at random (MAR).

For missing clinical improvement on D5V, D11V, or D28V, multiple imputations of missing clinical improvement on D5V, D11V, or D28V will be performed independently, and each subject will have their missing clinical improvement imputed independently of other subjects' imputations using a subject-specific imputation model. The pseudocode shown below details how missing data for clinical improvement for D5V (D11V or D28V) will be imputed using m multiply imputed datasets from linear models. The following covariates will be used non-missing for the MI model: treatment group, site indicators, age, gender, study day of D5V (centered at 5), presence of fever on Day 1, and presence of fever on D5V. The number of imputed, m , datasets will be chosen based on the average percent of missing data. Default value will be $m=20$ since sample size calculation assumed close to 20% drop-out rate.

As a first step to multiple imputation, an ordered list of variables to include in the subject-specific imputation model is constructed. Ordering is specified so that exact imputation results from final data are prespecified may be replicated in SAS (using seeds described below). The complete ordered list of variables for the imputation models for clinical improvement is below:

- Treatment Group (azithromycin is reference)
- Indicator of subject enrolled at the site with the second most number of subjects enrolled (binary indicator)
- Indicator of subject enrolled at the site with the third most number of subjects enrolled (binary indicator)
- Indicator of subject enrolled at the site with the fourth most number of subjects enrolled (binary indicator)
- Indicator of subject enrolled at the site with the least number of subjects enrolled (binary indicator)
 - Note: the site with the most number of subjects enrolled is reference for site. Language is written to allow for an arbitrary number of sites. In the event of a number of ties for the number of subjects enrolled, tied sites will be ordered in ascending alphanumeric order in the list of model variables.
- Age at enrollment
- Gender (Male is the reference)
- Study day of D5V (centered at 5)
- Presence of fever on Day 1 as recorded on the Assessment of LRTI Symptoms and Fever (LRT) form
- Presence of fever in the day preceding or at the D5V as recorded on Solicited Events or vital signs form

The actual list of MI model variables for each subject-specific imputation model will follow the ordering above but omit variables with missing values. The below pseudo-code / SAS code outlines the creation of 20 multiple imputation datasets. Note that the seeds used in the actual analysis must follow the specification given in the pseudo-code and subjects must be processed in the order described in the pseudo-code. The pseudo-code is for D5V, but the general logic is also applicable to D11V and D28V.

*Outcome variables: clinimprove_D5V

DEFINE i=index variable for subjects having clinical improvement imputed.

Subjects requiring imputation are sorted in ascending order by PATID.

DEFINE N=number of subjects requiring imputation

DEFINE g&i=analysis dataset containing predictors and clinical improvement for

ATP-5 subjects as well as subject i (only one subject not in ATP-5 included). Note that ATP-5 subjects that are missing a value for one or more variables in the subject-specific imputation model are excluded.

DEFINE imp_g&i = g&i, with 20 imputed values for the missing clinical improvement

added by PROC MI

DEFINE &&modelVars_&i = list of observed variables in subject i (treatment group, site1, site2, site3, site4, age, gender, cstday5, fever), to be used for imputation of clinical improvement

Step 1: Imputation model: This model will generate 20 datasets with each dataset containing original complete data along with imputed values for subjects with missing endpoint.

```
%do i=1 %to &N;
```

```
PROC MI data= g&i out= imp_g&i seed= 22131&i NIMPUTE=20 noprint;
```

```
  Var &&modelVars_&i clinimprove_D5V;
```

```
  monotone regression(clinimprove_D5V) = &&modelVars_&i;
```

```
run;
```

```
%end;
```

imp_g&i will be subset to contain only rows for the subjects with imputed clinical improvement and merged together and with ATP-5 data to create the twenty complete multiply imputed datasets

Step 2: Analysis model: This model will fit regression models to the 20 complete datasets to obtain parameter estimates for treatment success, clinical cure, microbiological success.

```
proc reg data= imp_g outest= out_clinimp_D5V covout noprint;
```

```
model clinimprove_D5V= trt cstday5/clb alpha=0.05;
```

```
by _imputation_;
```

```
run;
```

Step 3: Combine estimates from models in step 2 to obtain overall estimates summarized over 20 imputed datasets;

```
proc mianalyze data= out_clinimp
```

```
  _D5 alpha = 0.05;
```

```
modeleffects intercept trt cstday5;
```

```
ods output ParameterEstimates=parms_trts;
```

```
run;
```

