#### **11.4.1 Primary Analysis**

The non-inferiority of placebo versus azithromycin with respect to clinical improvement on at Visit 3 (as defined in Section 3.2.1), using a non-inferiority margin of 12.5%, will be determined for the ITT analysis population using a 95% confidence interval of the difference in proportions of clinical improvement as constructed using multiple imputation of clinical improvement with linear regression. The study Day that Visit 3 occurred on will be included as a covariate. A lower bound of the confidence interval greater than -12.5% will result in the conclusion of non-inferiority of placebo. At minimum, the imputation model will utilize available information collected at baseline and any completed study visits. Further details of the imputation model will be described in the SAP.

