5. SAMPLE SIZE CONSIDERATIONS

The null hypothesis corresponding to the primary analysis if this study is:

Null hypothesis: $\pi_{\text{placebo}} - \pi_{\text{azithromycin}} \leq -12.5\%$,

Alternative hypothesis (non-inferiority): $\pi_{\text{placebo}} - \pi_{\text{azithromycin}} > -12.5\%$,

where π represents the probability of clinical improvement at study day 5. 12.5% is the non-inferiority margin used for this study.

The study was first designed assuming that 840 subjects would have to be enrolled in order to randomize 420 (50%) subjects and have 80% power to rule out a 12.5% increase in the clinical improvement rate with antibiotic therapy compared to placebo assuming a clinical improvement rate of 80% in each group using a two-sided 95% confidence interval (CI) using normal approximation with continuity correction with continuity correction, in the according-to-protocol analysis population at D5V (ATP-5) as defined in Section 6.3 (i.e., allowing for 15% loss in each treatment group).

These assumptions underlying the original target sample size of 420 subjects were assessed by a planned, interim, blinded analysis after approximately 210 subjects completed or terminated from the study. The interim report was finalized on January 9th, 2020. The observed clinical improvement rate at the time of the interim analysis was 57.6% in each group which is lower than the initially assumed 80% rate. Due to this finding, new sample size estimates have been generated to account for actual observed rates of clinical improvement and protocol deviations that preclude inclusion in the primary analysis. The total sample size was increased to enroll 674 subjects which will allow 560 subjects eligible for the ATP-5 analysis population allowing for 16.9% loss in each treatment group to follow up/rescue medication. This new sample provides 80% power to rule out a 12.5% increase in the clinical improvement rate with antibiotic therapy compared to placebo assuming a clinical improvement rate of 57.6% in each group using a two-sided 95% CI with continuity correction, in an according-to-protocol analysis (i.e., allowing for 16.9% loss in each treatment group to follow up/rescue medication).

Although analysis using an ATP population was used for determination of sample size (to account for missing data), the primary analysis will be an ITT analysis using all randomized subjects.

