8. EFFICACY EVALUATION

All efficacy variables will be listed by subject. Data will be summarized by treatment group. Continuous efficacy variables will be summarized with the number of observations, mean, median, standard deviation, minimum, and maximum. Categorical efficacy variables will be summarized by number and percent in each category.

All statistical tests are performed at the $\alpha=0.05$ significance level. The primary hypothesis is a one-sided test but uses a two-sided 95% CI to make a conclusion about non-inferiority.

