8.1.1. Primary Analysis of Clinical Improvement at D5V Using ITT Population

The hypotheses corresponding to the primary analysis of this study are:

Null hypothesis: $\pi_{\text{placebo}} - \pi_{\text{azithromycin}} \leq -12.5\%$,

Alternative hypothesis(non-inferiority): $\pi_{\text{placebo}} - \pi_{\text{azithromycin}} > -12.5\%$,

where π represents the probability of clinical improvement at study D5V. 12.5% is the non-inferiority margin used for this study and is also used for all secondary non-inferiority analyses. The primary analysis alone will be used to conclude non-inferiority of placebo to azithromycin, while other analyses are supportive.

The non-inferiority of placebo versus azithromycin with respect to clinical improvement on at D5V using a non-inferiority margin of 12.5%, will be determined for the ITT analysis population using a two-sided 95% CI of the difference in proportions of clinical improvement as constructed using multiple imputation of clinical improvement with linear regression. The study day that D5V occurred on will be included as a covariate. A lower bound of the CI greater than -12.5% will result in the conclusion of non-inferiority of placebo. The imputation model will utilize available information collected at baseline and any completed study visits.

The primary analysis will use multiple imputation with a linear regression model without rounding to impute missing values of clinical improvement at D5V using the ITT population [9 and 10].

Although the linear regression without rounding can sometimes yield implausible imputed values of treatment success, Horton et.al (2003) [10] showed that this method yields an unbiased estimate of the binomial proportion.

- Let Y_1, Y_2, \dots, Y_N be independent and identically distributed (iid) Bernoulli random variables
- Let $p = E(Y_i)$ be the probability of success
- Assume that only n out of the N Bernoulli data points are observed; the rest are missing. For simplicity, assume Let Y_1, Y_2, \dots, Y_n are observed and Let Y_{n+1}, \dots, Y_N are missing. Further assume that data is Missing Completely at Random (MCAR).

For estimating p , the minimum variance unbiased estimate (MVUE) of p denoted by \hat{p} which is simply the mean of observed data, i.e.,

$$\hat{p} = \frac{1}{n} \sum_{i=1}^n Y_i$$

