8.2.2. Analysis of Clinical Improvement at D11V and D28V Using ITT Analysis Population

Analysis of clinical improvement will be repeated for D11V and D28V using the ITT analysis population in an analogous manner as the primary analysis as described in Section 8.1.1.

The non-inferiority of placebo versus azithromycin with respect to clinical improvement on at D11V will be determined for the ITT analysis population using a 95% CI of the difference in proportions of clinical improvement as constructed using multiple imputation of clinical improvement with linear regression. The study day that D11V (or D28V) occurred on centered at the planned study day (11 for D11V and 28 for D28V) will be included as a covariate in the imputation model. The imputation model will utilize available information collected at baseline and any completed study visits as described in Section 8.4.1.

Rates of clinical improvement for each treatment group in the ITT population along with their 95% CI and a point estimate of the difference in rates of clinical improvement at D5V along with a 95% CI will be obtained using linear regression following multiple imputation and shown in [Table 23](#) for D11V and [Table 25](#) for D28V after adjusting for study day of D11V and D28V, respectively.

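### The SAP list for imputing missing Day 11 and Day 28 clinical improvement leaves out the subject's own earlier outcome, although the Protocol and SAP 8.2.2 say completed visits will be used

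*SAP*

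**What the plan says.** Protocol 11.4.1 sets a floor: "At minimum, the imputation model will utilize available information collected at baseline and any completed study visits". Protocol 11.4.2, items 2 and 3, repeats that analysis at Visits 4 and 5. SAP 8.2.2 says the same for D11V and D28V and points to the details: "The imputation model will utilize available information collected at baseline and any completed study visits as described in Section 8.4.1".

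SAP 8.4.1 gives those details. It states that "multiple imputations of missing clinical improvement on D5V, D11V, or D28V will be performed independently", and names the covariates as "treatment group, site indicators, age, gender, study day of D5V (centered at 5), presence of fever on Day 1, and presence of fever on D5V". A bulleted list follows and is described as complete. The code is written for D5V and its logic is extended to D11V and D28V. A variable that a subject lacks is omitted from that subject's model. SAP 6.3.1 agrees with this narrower content: baseline variables plus fever at the time point being imputed.

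By contrast, the list for imputing DOOR in SAP 8.4.2 does include observed clinical improvement at D5V.

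On the use of these results, SAP 8.1.1 says: "12.5% is the non-inferiority margin used for this study and is also used for all secondary non-inferiority analyses". The same section makes the Day 5 ITT analysis the sole basis for concluding non-inferiority and calls the others supportive.

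**The concern.** Consider a subject who attends Visit 3, is scored a failure, and is then lost. D11V symptoms and fever both come from the study-day-11 diary record, and D28V symptoms and fever both come from the Visit 5 form (SAP 6.5.2). If the record is absent, fever is missing too and drops out of the model. Study day is set to the planned day (SAP 3.3.1). What remains is arm, site, age, gender, a constant and Day 1 fever. The known failure plays no part.

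SAP 8.4.1 assumes data are missing at random, but that assumption is conditional on what is in the model. If loss depends on the Day 5 result, and the Day 5 result predicts Day 11, the listed covariates do not make it hold. If that dependence differs between arms, the difference tested against -12.5% in secondary objectives 6 and 7 is shifted, and Tables 23 and 25 print a Yes/No non-inferiority conclusion from it.

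**Working it through.** **No plan figure to reproduce.** The sample-size text covers Day 5 only. The documents give no Day 11 or Day 28 response rate, no missing share for those visits and no dropout by Day 5 outcome.

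**Inputs from the documents**
- Margin 12.5 points (SAP 8.1.1).
- Day 5 rate: "assuming a clinical improvement rate of 57.6% in each group using a two-sided 95% CI with continuity correction" (SAP 5).
- Alternative placebo Day 5 rate at the margin: 57.6 - 12.5 = 45.1%.

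**Assumed inputs**
- Day 11 success 90-95% after Day 5 success (ps) and 50-65% after Day 5 failure (pf).
- Dropout before Day 11: 8-10% after Day 5 success (ms), and varied by arm after Day 5 failure (mf).
- Every Day 11 dropout has an observed Day 5 outcome.
- The remaining covariates (site, age, gender, Day 1 fever) carry no information about it.

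**Formulas, per arm, with p5 the Day 5 success rate**
- True Day 11 rate = p5·ps + (1 - p5)·pf.
- Rate implied by imputation that ignores Day 5 = [p5(1 - ms)ps + (1 - p5)(1 - mf)pf] / [p5(1 - ms) + (1 - p5)(1 - mf)].
- Shift = (placebo minus azithromycin, implied) - (placebo minus azithromycin, true).

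**Worked case: p5 = 0.576 in both arms, ps = 0.90, pf = 0.50, ms = 0.10**
- True rate in each arm: 0.576 × 0.90 + 0.424 × 0.50 = 0.7304. The true difference is 0.
- Azithromycin, mf = 0.15: (0.5184 × 0.90 + 0.3604 × 0.50) / 0.8788 = 0.7360.
- Placebo, mf = 0.25: (0.5184 × 0.90 + 0.3180 × 0.50) / 0.8364 = 0.7479. Shift +1.2 points.
- Placebo, mf = 0.35: (0.5184 × 0.90 + 0.2756 × 0.50) / 0.7940 = 0.7612. Shift +2.5 points.
- mf = 0.25 in both arms: shift 0.
- mf = 0.25 on azithromycin and 0.15 on placebo: shift -1.2 points.

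**Over all the stated input ranges**

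| Failure dropout, azithromycin v placebo | Shift toward placebo | Share of 12.5 points |
|---|---|---|
| 15% v 25% | 0.7 to 1.4 points | 6-11% |
| 12-15% v 32-35% | 1.3 to 3.4 points | 10-27% |
| equal (15%, 25% or 35% in both arms) | 0 to 0.2 points | up to 2% |

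**Effect on the test.** A simulation used 337 per arm, 20 imputations by linear regression without rounding, Rubin's rules, 2,000 trials per setting and a true difference of -12.5 points. It assumed 16.9% missing and, except where stated, azithromycin dropout unrelated to outcome. With placebo failures leaving at 2 to 3 times the rate of placebo successes, and a gap between ps and pf of 0.2 to 0.6, false non-inferiority was 4.6-11.4% against a nominal 2.5%. With the Day 5 outcome added to the model it was 2.2-2.9%. When failures left at 3 times the success rate in both arms, the planned model gave 2.6%. When this happened on azithromycin only, it gave 0.4%.

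The 16.9% is borrowed: in the SAP it is the allowance for subjects not eligible for ATP-5, not the share of ITT subjects with a missing Day 11 outcome.

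**The case against.** **Separate runs do not exclude earlier outcomes.** A reader might infer that imputing each time point independently forbids earlier outcomes. It does not, since a separate D11V run can include D5V as a covariate. The evidence is the closed list, not that word.

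**The stakes are limited.** These tests are supportive, and Tables 28 and 29 give tipping-point grids from 0% to 100% imputed success separately by arm, which cover the feared case. That stands. The grids show the sensitivity but leave the estimate and the Yes/No line in Tables 23 and 25 as they are. The unimputed ATP-11 and ATP-28 analyses carry the same selection.

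**No differential dropout is documented.** The trial is double-blind, and nothing shows that failures leave more often on placebo. That stands, so direction and size are conditional.

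**Some Day 5 failures may carry forward.** An antibiotic-treated medically attended visit or hospitalization counts at any time after randomization, and SAP 6.5.2.3 scores it present without requiring the later visit. Such subjects may not need imputation, but the SAP does not say how the composite is scored when other components are missing. Vital signs also do not count at Day 11, so a Day 5 failure on pulse alone need not predict Day 11 failure.

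**Fever might be carried over.** Read literally, the list could bring D5V fever into the later models. SAP 6.3.1 points the other way, and fever is only one component of the Day 5 outcome.

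**Conclusion.** The inconsistency is established from the text. SAP 8.4.1 does not deliver what Protocol 11.4.1 and SAP 8.2.2 promise, and it departs from the SAP's own DOOR list. The consequence is conditional. If Day 5 failures are lost more often on placebo, the Day 11 and Day 28 ITT differences move toward non-inferiority. For Day 11, the illustrative size is 0.7-1.4 points at 15% v 25% failure dropout and 1.3-3.4 points at 12-15% v 32-35%. These figures assume that every dropout has an observed Day 5 outcome, so they shrink to the extent that Day 11 dropouts have none.

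Two stronger readings are not supported. One is that the plan is biased in favor of placebo: the shift is about zero with matching dropout patterns and reverses if failures leave more often on azithromycin, and the documents do not say which will occur. The other is that the trial's conclusion is at risk: the Day 5 ITT analysis alone decides that, and this point does not touch it.

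**What to change.** In SAP 8.4.1, write out the D11V and D28V lists. Add observed clinical improvement at D5V to the D11V list, and observed clinical improvement at D5V and at D11V to the D28V list. Keep the rule that omits a variable missing for the subject. The word on independent imputation can stay, and the analysis models do not change. State also how the composite is scored when the medical-visit component has failed and other components are missing.

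No new data are needed, because these outcomes are already derived. There is a small cost. SAP 8.4.1 excludes donors who lack any variable in a subject's model, and ATP-11 and ATP-28 do not require a completed D5V, so some donors will be lost, and more for D28V if both earlier outcomes are used. Subjects with no observed earlier outcome are imputed as before and gain nothing.
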